6.5.1 Dose modifications

For subjects who do not tolerate the protocol-specified dosing schedule, dose interruptions and/or reductions are either recommended or mandated in order to allow subjects to continue ruxolitinib.

These dose modifications are summarized in [Table 6-3](#). Deviations to mandatory dose interruptions and/or reductions are not allowed. Permanent treatment discontinuation is mandatory for specific events indicated as such in [Table 6-3](#).

Based on the subject's age, the ruxolitinib dose will not exceed the starting dose level defined for that age Group. The dose for CNI and/or corticosteroids can be modified as per Investigator discretion, institutional guidelines, or as per product label.

A standardized dosing paradigm in [Table 6-4](#) and [Table 6-5](#) will be used to determine dose adjustments for safety and efficacy so that each subject is titrated to their most appropriate dose. These dose changes must be recorded on the Dosage Administration Record eCRF.

A more frequent schedule of safety assessments is recommended (i.e. every 2 weeks) after restarting ruxolitinib due to a dose hold.

If a subject requires a dose interruption of > 21 days from ruxolitinib, then the subject must be permanently discontinued from ruxolitinib, and will be entered into early discontinuation follow-up with assessments as described in [Table 8-1](#).

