6.5.1.2 Dose adjustments for ruxolitinib non-hematologic safety

Dose reductions or interruptions for non-hematologic toxicity attributed to ruxolitinib are permitted in order to allow the subject to continue on ruxolitinib. Dose adjustments for different ranges of non-hematologic toxicity are described in [Table 6-3](#). The objective of the dose adjustment rules is to optimize treatment response for each individual subject while avoiding significant non-hematologic toxicities.

As organ toxicities are relatively common in alloSCT subjects, any adverse event must be assessed to determine whether it is suspected to be related to ruxolitinib treatment. Ruxolitinib dose adjustments are only required for adverse events that are suspected to be related to the study drug. This has particular relevance in evaluation of elevated serum creatinine, as

elevations related to CNI administration are often seen. Dose adjustment of CNI will follow institutional guidelines and investigator judgement, with CNI dose reductions anticipated if rising creatinine occurs, to potentially alleviate the need for ruxolitinib dose reductions.

Treatment with ruxolitinib may be delayed up to 21 days to allow for resolution of toxicity. Subjects may resume treatment if no medical condition or other circumstance exists that, in the opinion of the Investigator, would make the subject unsuitable for further participation in the study.

Ruxolitinib must be permanently discontinued upon any one of the following non-hematological adverse events attributed to study drug that fails to resolve to Grade 2 or better within 14 days or if a lower re-start dose or administration schedule subsequent to any of the following non-hematologic toxicities is either not available or likely to be clinically ineffective:

- occurrence of a Grade 4 laboratory or non-laboratory abnormality attributable to ruxolitinib
- occurrence of a Grade 3 laboratory or non-laboratory abnormality attributable to ruxolitinib that remains at Grade 3 or worse for greater than 14 days

If any one or more of the treatment discontinuation criteria are met prior to Cycle 7 Day 1, the subject will be considered to be a non-responder in terms of the primary endpoint.

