Grade 1 (> ULN - 1.5 x ULN)	Recommendation: Maintain dose level.
Grade 2 (> 1.5 - 3.0 x ULN)	Mandatory: Reduce 1 dose level until resolved to ≤ Grade 1 or baseline, then resume initial dose level.
Grade 3 (> 3.0 - 6.0 x ULN)	Mandatory: Hold dose until resolved to ≤ Grade 2, then restart at reduced 1 dose level. If resolves to ≤ Grade 1, can resume initial dose level.
Grade 4 (> 6.0 x ULN)	Mandatory: Discontinue subject from study treatment.
Investigations (Hepatic)	
Total Bilirubin elevation	
> ULN - 1.5 x ULN	Recommendation: Maintain dose level.
> 1.5 - 3.0 x ULN	Recommendation: Maintain dose level.
> 3.0 - 10.0 x ULN*	Mandatory: Interrupt treatment. Monitor LFTs ^b weekly or more frequently if clinically indicated, until resolved to ≤ 3.0 x ULN: If resolved in ≤ 14 days, then resume same dose level. If resolved in > 14 days, then resume at reduced one dose level.
> 10.0 x ULN*	Mandatory: Interrupt treatment. Monitor LFTs ^b weekly, or more frequently if clinically indicated, until resolved to ≤ 3.0 x ULN: If resolved in ≤ 14 days, then resume at reduced 1 dose level. If resolved in > 14 days, then discontinue subject from study treatment. The subject should be monitored weekly (including LFTs ^b), or more frequently if clinically indicated, until total bilirubin has resolved to baseline or stabilization over 4 weeks.
AST or ALT elevation	
> ULN - 3.0 x ULN	Recommendation: Maintain treatment and dose level.
If normal at baseline: > 5.0 x ULN for more than 2 weeks, OR > 10 x ULN If elevated at baseline: >3 x baseline and > 10 x ULN	Mandatory: Interrupt treatment. Repeat LFTs ^b as soon as possible, preferably within 48-72 hours from awareness of the abnormal results; Monitor LFTs ^b weekly, or more frequently if clinically indicated, until resolved to ULN or to baseline. : If resolved, then resume at reduced one dose level.

Dose modifications for ruxolitinib for adverse events^a suspected to be drug-related	
Worst toxicity	
> 20.0 x ULN:	Mandatory: Permanently discontinue patient from study treatment.. Repeat LFTs ^b as soon as possible, preferably within 48-72 hours from awareness of the abnormal results; monitor LFTs ^b weekly, or more frequently if clinically indicated, until resolved to baseline or stabilization over 4 weeks.
Combined ^celevations of AST or ALT and total bilirubin	

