Grade 1	Recommendation: Maintain dose level.
Grade 2	Recommendation: Maintain dose level.
Grade 3	Recommendation: Reduce 1 dose level until resolved to ≤ Grade 2, then: If resolved in ≤ 7 days, increase by one dose level. If resolved in > 7 days, then maintain the reduced dose level.
Grade 4	Mandatory: Discontinue subject from study treatment.
Other adverse events	
Grade 1 or 2	Recommendation: Maintain dose level.
Grade 3	Recommendation: Hold dose until ≤ grade 2, then decrease 1 dose level
Grade 4	Recommendation: Discontinue subject from study treatment.
All dose modifications should be based on the worst preceding toxicity.	
For dose level refer to Table 6-3 and Table 6-4	
^a Common Terminology Criteria for Adverse Events (CTCAE Version 4.03)	
^b Core LFTs consist of ALT, AST, GGT, total bilirubin (fractionated (direct and indirect), if total bilirubin > 2.0 x ULN), and alkaline phosphatase (AP) (fractionated (quantification of isoforms), if alkaline phosphatase > 2.0 x ULN.)	
^c "Combined" defined as total bilirubin increase to the defined threshold concurrently with ALT/AST increase to the defined threshold.	
If combined elevations of AST or ALT and total bilirubin do not meet the defined thresholds, please follow the instructions for isolated elevation of total bilirubin and isolated elevation of AST/ALT, and take a conservative action based on the degree of the elevations (e.g. discontinue treatment at the situation when omit dose is needed for one parameter and discontinue treatment is required for another parameter). After all elevations resolve to the defined thresholds that allow treatment re-initiation, re-start the treatment either at the same dose or at one dose lower if meeting a criterion for dose reduction.	
^d "Cholestasis" defined as ALP elevation (> 2.0 x ULN and R value < 2) in patients without bone metastasis or elevation of ALP liver fraction in patients with bone metastasis	
Note: The R value is calculated by dividing the ALT by the ALP, using multiples of the ULN for both values. It denotes whether the relative pattern of ALT and/or ALP elevation is due to cholestatic (R ≤ 2), hepatocellular (R ≥ 5), or mixed (R > 2 and < 5) liver injury	

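### If bilirubin >3.0–10.0 × ULN is Grade 3, Table 6-3 directs a restart and Section 6.5.1.2 a permanent stop once a drug-attributed elevation outlasts 14 days, and the child's primary-endpoint status is defined inconsistently

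*Protocol*

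**What the plan says.** Protocol Table 6-3 covers events suspected to be drug-related. Its row for total bilirubin >3.0–10.0 × ULN is headed as mandatory. Treatment is interrupted until the value is 3.0 × ULN or lower. After recovery within 14 days the same dose is resumed; otherwise: "If resolved in > 14 days, then resume at reduced one dose level". The row sets no upper time limit.

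Section 6.5.1.2 states: "Ruxolitinib must be permanently discontinued upon any one of the following non-hematological adverse events attributed to study drug", where the event does not improve to Grade 2 or better within 14 days. One of the listed events is "occurrence of a Grade 3 laboratory or non-laboratory abnormality attributable to ruxolitinib that remains at Grade 3 or worse for greater than 14 days". The same section adds an endpoint rule. It begins "If any one or more of the treatment discontinuation criteria are met prior to Cycle 7 Day 1" and concludes that the child is a non-responder for the primary endpoint.

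Section 6.5.1 adds two general rules: "Deviations to mandatory dose interruptions and/or reductions are not allowed", and "If a subject requires a dose interruption of > 21 days from ruxolitinib, then the subject must be permanently discontinued from ruxolitinib".

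On the analysis side, protocol Section 12.4.3 and SAP Section 2.5.3 name two routes to non-response: a missing assessment that prevents evaluation, and new systemic therapy before Cycle 7 Day 1. SAP Section 2.5.1 takes the response from the CRF. None of these sections repeats the Section 6.5.1.2 rule, and SAP Section 4, which lists changes from the protocol, does not say it was dropped.

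**The concern.** A site with a child whose drug-attributed bilirubin has stayed above 3.0 × ULN for more than 14 days finds a restart in one place and a permanent stop in another. The choice determines whether the child is exposed to ruxolitinib again.

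It also bears on the primary endpoint. Suppose the event falls before Cycle 7 Day 1, the child restarts, and a CR or PR is recorded at that visit. Section 6.5.1.2 counts that child as a non-responder; protocol Section 12.4.3 and the SAP count a responder. The endpoint mismatch is not specific to bilirubin. It arises for any discontinuation criterion met before Cycle 7 Day 1, and the bilirubin row is where a child can most readily meet a criterion and still be on treatment.

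**Working it through.** **Step 1. Is the band Grade 3?** The bilirubin rows carry no grade labels and the documents print no bilirubin grades, so this is an assumption. Three features support it:
- The band is the third of four ascending bands. In the nearby creatinine and amylase/lipase rows the third band is labelled Grade 3.
- Its recovery target, 3.0 × ULN, is the top of the second band, which fits the Grade 2 target in Section 6.5.1.2.
- Footnote a to Table 6-3 adopts CTCAE 4.03.

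If the band were Grade 4, the 14-day limit in Section 6.5.1.2 would still conflict with the row. Only Grade 2 or lower would remove the conflict.

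**Step 2. The passages by time to recovery**, taking the hold to start when the elevation is found:

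| Recovery to ≤3.0 × ULN | Table 6-3 row | Section 6.5.1.2 | Section 6.5.1 hold limit |
|---|---|---|---|
| Day 14 or earlier | resume same dose | stop rule not met | not reached |
| Days 15–21 | resume one level lower | permanent stop | not reached |
| After day 21 | resume one level lower | permanent stop | permanent stop |

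The row above 10.0 × ULN does direct discontinuation after 14 days, in line with Section 6.5.1.2. The row below that threshold does not.

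**Step 3. Which children are in scope.** Both rules apply only to events attributed to ruxolitinib. A footnote to Table 6-3 gives a separate path for elevations that are indirect only, with hemolysis ruled out.

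**Step 4. The plan's own figure.** Table 12-1 for 42 children, at least 27 responders and a true ORR of 0.70:
- P(X ≥ 27), X ~ Binomial(42, 0.70) = 0.8360; the plan states 0.836.
- Exact 90% limits for 27/42 = 0.5045 to 0.7653; the plan states 0.505 to 0.765.

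It reproduces, as does the 46-child row: P(X ≥ 30) = 0.809, lower limit 0.5208.

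**Step 5. Size per child.** The protocol reports 46 enrolled. The FAS may be smaller, because SAP Table 2-3 excludes children with certain protocol deviations. For a child with a recorded CR or PR whose status changes:
- FAS of 46: 1/46 = 2.2 points. FAS of 42: 1/42 = 2.4 points.
- The number of such children is not given. As a range at 46: one, 2.2 points; two, 2/46 = 4.3 points; three, 3/46 = 6.5 points.

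**The case against.** The strongest reply is that the hepatic rows are a deliberate, specific rule. Amendment 1 revised Table 6-3 to allow for liver involvement by GvHD, the bilirubin rows are ungraded, and Section 6.5.1 ties mandatory permanent discontinuation to events so marked in the table. This row is not so marked. That leans toward the table, but it is not a precedence rule: Section 9.1.1 keeps adverse-event discontinuations under Section 6.5.1 in force alongside those in Table 6-3.

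Four stronger readings are tempting, and the documents do not support them.
- *Sites face two mandatory orders and cannot comply with both.* Section 6.5.1 bars deviation from interruptions and reductions; it does not compel a restart. Section 6.5.1.2 is permissive: "Subjects may resume treatment if no medical condition or other circumstance exists". A site that interrupts and then stops has met the mandatory interruption. A directed restart still contradicts a required stop.
- *The endpoint status is undefined.* It is defined twice, with different answers.
- *Liver cGvHD makes this common.* Bilirubin caused by cGvHD triggers neither rule. Liver involvement makes attribution harder, but the documents give no frequency.
- *One child could decide the trial.* At 46, the 90% lower limit is 0.521 for 30 responders and 0.499 for 29, so one child crosses 50% only if the count is exactly 30. The 50% figure is a sample-size benchmark, and no hypothesis is tested.

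It is also true that early-discontinuation follow-up in Section 9.1.1 lists no cGvHD response assessment. A child who stopped will probably lack a Cycle 7 Day 1 response and be a non-responder on either rule.

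**Conclusion.** The contradiction stands, conditional on the >3.0–10.0 × ULN band being Grade 3 or higher. It covers drug-attributed, not purely indirect, bilirubin that resolves after more than 14 days. Between the two passages alone the window is days 15 to 21; beyond that the row also fails to reflect the 21-day limit. The endpoint inconsistency is separate from the grade assumption and applies to every discontinuation criterion.

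The effect on the estimate is probably small: about 2.2 ORR points per affected child with a recorded response, if the FAS is 46, and zero if no such child exists. It falls on the estimate and its interval only. The SAP's sensitivity analysis in Section 2.5.4 would not isolate these children. It names holds beyond 21 days without discontinuation, but has no specific item for a 15-to-21-day hold followed by a restart.

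**What to change.** 1. Reconcile the bilirubin row of Table 6-3 with Section 6.5.1.2, and with the 21-day limit in Section 6.5.1, so that one action is stated. The sponsor's hepatic-safety experts decide which; no view is taken here. This is a sentence or a row edit. Enrollment was complete in September 2021, so it can no longer change how children were managed before Cycle 7 Day 1.
2. State whether the non-responder rule in Section 6.5.1.2 applies in the primary analysis. If it does, add it to SAP Section 2.5.3; if not, record that in SAP Section 4.
3. In the CSR, list any child with drug-attributed bilirubin >3.0–10.0 × ULN lasting more than 14 days before Cycle 7 Day 1, with the action taken. Where a Cycle 7 Day 1 response was recorded, show ORR with that child counted under each rule.

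The cost is two short text changes and one small listing from bilirubin, dosing and response data already collected. If no child qualifies, one sentence in the CSR closes the bilirubin point.

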For participants with normal baseline ALT and AST and total bilirubin value: AST or ALT > 3.0 x ULN combined with total bilirubin > 2.0 x ULN without evidence of cholestasis ^d OR For participants with elevated baseline AST or ALT or total bilirubin value: [AST or ALT > 3 x baseline OR [> 8.0 x ULN], whichever is lower combined with Total bilirubin > 2 x baseline AND >2.0 x ULN Note: For participants with Gilbert's syndrome, at least 2-fold increase in direct bilirubin	Mandatory: Interrupt treatment and adjudicate for DILI: Repeat as soon as possible, preferably within 48 hours from awareness of the abnormal results, then with weekly monitoring of LFTs ^b , or as clinically indicated, until AST, ALT, or total bilirubin have resolved \leq ULN or to baseline. Refer to Section 6.5.2.1 (for additional follow-up evaluations as applicable.) If causality assessment indicates that DILI is probable: Permanently discontinue participant from treatment. If not DILI: Treat the identified cause according to institutional guidelines. Once resolved, resume at reduced one dose level.
Investigation (metabolic)	
Asymptomatic amylase and/or lipase elevation**	
Grade 1 (> ULN - 1.5 x ULN)	Recommendation: Maintain dose level.
Grade 2 (> 1.5 - 2.0 x ULN)	Recommendation: Maintain dose level.
Grade 3 (> 2.0 - 5.0 x ULN)	Recommendation: Hold dose of until resolved to Grade \leq 2, then: If resolved in \leq 7 days, then resume same dose level. If resolved in > 7 days, then resume at reduced 1 dose level.
Grade 4 (> 5.0 x ULN)	Recommendation: Discontinue subject from study treatment.
Vascular disorders	
Hypertension	
CTCAE Grade 3	Recommendation: Reduce 1 dose level until resolved to \leq Grade 2, then increase by one dose level.
CTCAE Grade 4	Mandatory: Discontinue subject from study treatment.
Gastro intestinal	
Pancreatitis	
Grade 2	Recommendation: Maintain dose level.
Grade \geq 3	Mandatory: Discontinue subject from study treatment.
Diarrhea***	
Grade 1	Recommendation: Maintain dose level. May initiate anti-diarrhea treatment.
Grade 2	Recommendation: Maintain dose level. May initiate anti-diarrhea treatment.
Grade 3	Recommendation: Reduce 1 dose level until resolved to \leq Grade 2, then increase by one dose level.
Grade 4	Mandatory: Discontinue subject from study treatment.
Skin and subcutaneous tissue disorders	
Rash/photosensitivity	

Dose modifications for ruxolitinib for adverse events^a suspected to be drug-related	
Worst toxicity	

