* Note: If total bilirubin > 3.0 x ULN is due to the indirect (non-conjugated) component only, and hemolysis as the etiology has been ruled out as per institutional guidelines (e.g., review of peripheral blood smear and haptoglobin determination), then reduce 1 dose level and continue treatment at the discretion of the Investigator.	
** Note: A CT scan or other imaging study to assess the pancreas, liver, and gallbladder must be performed within 1 week of the first occurrence of any ≥ Grade 3 of amylase and/or lipase. If asymptomatic Grade 2 elevations of lipase and/or amylase occur again at the reduced dose, subjects will be discontinued permanently from study treatment.	
*** Note: antidiarrheal medication is recommended at the first sign of abdominal cramping, loose stools or overt diarrhea	

Table 6-4 Dose reduction steps for ruxolitinib

Dose Reduction steps of ruxolitinib *			
Groups	Starting dose level – 0	Dose level – 1	Dose level – 2
Group 1	10 mg BID	5 mg BID	5 mg QD**
Group 2	5mg BID	5 mg QD or 2.5mg BID	Not applicable

Dose Reduction steps of ruxolitinib *			
Group 3	4 mg/m ² BID	50% of starting dose BID	Not applicable
Group 4	Starting dose BID***	50% of starting dose BID	Not applicable
*Dose reduction should be based on the worst toxicity demonstrated at the last dose.			
**Dose reduction below 5 mg total daily dose is not allowed.			
***Based on prior data collected from [CINC424F12201] and [CINC424C2301], [CINC424D2301].			

Subjects who have had a dose reduction of ruxolitinib in order to manage toxicity may resume treatment at the previous dose if hematologic/non-hematologic parameters meet the required threshold(s).

Table 6-5 Dose re-escalation levels for ruxolitinib

Dose Re-escalation*			
	Current dose	First dose escalation	Second dose escalation
Group 1	5 mg QD	5 mg BID	10 mg BID
	5 mg BID	10 mg BID	*
Group 2	5mg QD or 2.5 mg BID	5mg BID	Not applicable
Group 3	50% of starting dose BID	Starting dose BID	Not applicable
Group 4	50% of starting dose BID	Starting dose BID	Not applicable

Except for Group 1, all other dose escalations are examples and may not reflect the actual starting dose.
*Dose increases may not exceed 10 mg BID, in increments of 5 mg and not more often than every 2 weeks.

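### Read literally, Table 6-3 permanently stops ruxolitinib for a recurrent Grade 2 lipase or amylase rise but resumes it after a short recurrent Grade 3; a lesser gap is the missing AST/ALT floor in the combined liver rule

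*Protocol*

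**What the plan says.** Table 6-3 covers adverse events suspected to be drug-related, and Protocol 6.5.1.2 repeats that limit: "Ruxolitinib dose adjustments are only required for adverse events that are suspected to be related to the study drug".

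**Asymptomatic lipase/amylase.** Grade 2 (>1.5 to 2.0 x ULN) keeps its dose. Grade 3 (>2.0 to 5.0 x ULN) carries a recommendation that begins "Hold dose of until resolved to Grade" 2 or below. If that takes at most "7 days, then resume same dose level. If resolved in > 7 days, then resume at reduced 1 dose level". Grade 4 carries a recommendation to discontinue. A note attached to the heading of this block asks for imaging at Grade 3 or above and then adds: "If asymptomatic Grade 2 elevations of lipase and/or amylase occur again at the reduced dose, subjects will be discontinued permanently from study treatment". A general note to the table reads "All dose modifications should be based on the worst preceding toxicity".

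The text of 6.5.1.2 requires a permanent stop for, among others, "occurrence of a Grade 3 laboratory or non-laboratory abnormality attributable to ruxolitinib that remains at Grade 3 or worse for greater than 14 days". When a discontinuation criterion is met before Cycle 7 Day 1, "the subject will be considered to be a non-responder in terms of the primary endpoint".

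**Combined AST/ALT and bilirubin.** With AST, ALT and bilirubin all normal at baseline, the trigger is "AST or ALT > 3.0 x ULN combined with total bilirubin > 2.0 x ULN without evidence of cholestasis". If any one of the three was raised at baseline, the transaminase limb becomes the lower of 3 x baseline and 8 x ULN. Bilirubin must then exceed both 2 x baseline and 2.0 x ULN. Protocol 6.5.2.1 gives the same elevated-baseline threshold. Meeting the rule means mandatory interruption and adjudication for drug-induced liver injury (DILI). If DILI is probable, treatment stops for good; if it is not DILI, treatment restarts one dose level lower.

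**The concern.** A stopping rule should not become more lenient as the toxicity worsens. At the reduced dose, the lipase/amylase note ends treatment for a value that the rows tolerate, while a higher value can be followed by a restart. A site cannot tell whether the grade in the note is intended or a slip.

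The liver rule raises a smaller version of the same question. Two children with the same ALT course can be handled differently only because a different analyte was raised at baseline. Raised baselines are to be expected here, since Protocol 4.5 does not let liver tests exclude a child.

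What is at stake is unneeded loss of drug. Protocol 6.5.1.4 expects symptoms of cGvHD flare after abrupt interruption, although it allows tapering or corticosteroid cover. A permanent stop before Cycle 7 Day 1 is also counted as non-response.

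**Working it through.** The plan states no figure on this point, so there is none to reproduce. The first part compares texts; the second is simple arithmetic on the stated thresholds.

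**1. Lipase/amylase recurring at the reduced dose**

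| Recurrence | Action | Source |
|---|---|---|
| Grade 2 | permanent stop | note to Table 6-3 |
| Grade 3, back to Grade 2 or below in ≤ 7 days | hold, then same dose | Grade 3 row |
| Grade 3, back in > 7 to 14 days | hold, then one level lower | Grade 3 row |
| Grade 3 lasting > 14 days | permanent stop | 6.5.1.2 |
| Grade 4 | discontinue (recommended) | Grade 4 row |

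The second line is the clear inversion. The third line also inverts in Group 1, where Table 6-4 has a further level (5 mg once daily). Groups 2 and 3 have no lower level, so the row gives no usable restart dose there.

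Within these rows, the only way to a reduced dose is a Grade 3 that took more than 7 and at most 14 days to resolve. A child may also be at a reduced dose because of another toxicity.

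Neighbouring rules point the same way. Grade 2 pancreatitis keeps its dose, and 6.5.1.2 treats return to Grade 2 within 14 days as adequate recovery.

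**2. Combined rule, elevated-baseline branch**

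Let b be the child's baseline ALT in x ULN. The values of b are illustrative.

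- Current trigger = min(3b, 8).
- With a floor = max(3, min(3b, 8)).
- Trigger when all three analytes were normal at baseline = 3.0.

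| b | current trigger | with floor |
|---|---|---|
| 0.25 | 0.75 | 3.0 |
| 0.33 | 1.0 | 3.0 |
| 0.5 | 1.5 | 3.0 |
| 0.75 | 2.25 | 3.0 |
| 1.0 | 3.0 | 3.0 |
| 2.0 | 6.0 | 6.0 |
| 4.0 | 8.0 | 8.0 |

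Below b = 1.0 the limb is met under 3.0 x ULN. Below b = 1/3 it can be met by an ALT still within the normal range. The floor changes nothing at b = 1.0 or above. The same holds for AST.

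The bilirubin limb, max(2 x baseline, 2.0), must be met as well. Example: AST stays normal, ALT goes from 0.5 to 1.6 x ULN (1.6/0.5 = 3.2-fold), and bilirubin reaches 2.3 x ULN.

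- Baseline bilirubin 0.9: this is the fully normal branch and ALT is below 3.0, so both isolated rows say maintain.
- Baseline bilirubin 1.1: 2.3/1.1 = 2.09, and 2.3 exceeds 2.0, so interruption is mandatory.

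Above 3.0 x ULN the isolated bilirubin row also interrupts, but up to 10.0 it resumes the same dose if resolved within 14 days. The combined row adds DILI adjudication and restarts one level lower, so the actions still differ.

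**3. Endpoint**

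With 46 enrolled and all of them in the Full Analysis Set, one child is 1/46 = 2.17 percentage points.

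**The case against.** **On lipase/amylase.** The note may be a deliberately stricter rule for recurrence. It sits on the heading of the whole block, and a reader could take Grade 2 to mean Grade 2 or worse, which would remove the inversion. That reading is reasonable, but the sentence names Grade 2 alone and the Grade 3 row still provides for a restart. The rows are labelled as recommendations, and the note carries no label saying it is mandatory. It does say that subjects will be discontinued, however, so a site would probably act on it.

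Two stronger readings are tempting and fail. One is that a child restarted while still at Grade 2 must be stopped at once. The note requires the elevation to occur again, so a residual Grade 2 at restart is not a recurrence. The other is that a Grade 2 could never have come before: a child may pass through Grade 2 while recovering, or have had it at full dose before a reduction for another toxicity. Nor do the documents show that Grade 3 was the intended word.

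**On the liver rule.** A reader might call it internally inconsistent. It is not, because Table 6-3 and 6.5.2.1 agree. Amendment 1 revised the liver rules with liver GvHD in mind, a sensitive trigger is defensible, and any split by baseline creates a step. All of that stands. What remains is an omitted floor: the bilirubin limb and the isolated AST/ALT interruption row both carry a minimum in x ULN, and this limb does not.

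**Conclusion.** Both points hold and both are minor. The lipase/amylase note, taken as written, gives the milder grade the harsher action. The liver rule lacks an AST/ALT floor and therefore over-triggers; it misses no liver injury.

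No bias in the reported response rate can be inferred, because the documents do not say how often either rule was used. The 2.2 points per child need three things: all 46 children in the Full Analysis Set (the SAP removes any child treated beyond local regulatory requirements), a permanent stop before Cycle 7 Day 1, and a child who would otherwise have responded.

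A reader might also infer that every interruption under the liver rule makes a non-responder. It does not. The non-responder rule concerns discontinuation, which follows if DILI is judged probable or if the hold exceeds 21 days (6.5.1).

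**What to change.** - **Lipase/amylase note.** Have the clinical team confirm the intended grade. Preferably change it to Grade 3 or higher recurring at the reduced dose, which agrees with the Grade 2 row and with 6.5.1.2 on recovery. Failing that, write Grade 2 or higher and align the Grade 3 row for recurrences at the reduced dose.
- **Combined liver rule.** In Table 6-3 and 6.5.2.1, require AST or ALT above the lower of 3 x baseline and 8 x ULN, and also above 3 x ULN. Alternatively, choose the branch by that transaminase's own baseline. Keep the 8 x ULN limb: without it, a baseline of 4.0 x ULN would need 12.0.

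The cost is one note (or the note and one row), one table row and one bullet, made by amendment under Protocol 14.1. Few children can still benefit. With enrollment complete on 17-Sep-2021 and up to 28 days of screening, the latest first dose is about 15-Oct-2021. Adding 39 x 28 = 1092 days gives about 10-Oct-2024, against an SAP date of 07-Oct-2024. The wording therefore matters mainly if the table is reused.

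Matching the recorded reasons for dose change and discontinuation to the graded laboratory listings would show whether any of the at most 46 children was affected. That needs no new data, but by itself it changes no result. The documents do not say that DILI adjudication outcomes are held in the database.
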